12.2 Definitions

12.2.1 Adverse Event (AE)

Any untoward or unfavorable medical occurrence associated with the subject's participation in the research, whether or not considered related to the subject's participation in the research (modified from the definition of adverse events in the 1996 International Conference on Harmonization E-6 Guidelines for Good Clinical Practice) (from OHRP "Guidance on Reviewing and Reporting Unanticipated Problems Involving Risks to Subjects or Others and Adverse Events (1/15/07)"

<http://www.hhs.gov/ohrp/policy/advevtguid.html#Q2>)

For this study, an adverse event will include any untoward or unfavorable medical occurrence associated with:

- **Study therapy regimen:** Rituximab or Rituximab Placebo
- **Study mandated procedures:**
 - Bronchoscopy: Any AE occurring within 24 hours after a study related bronchoscopy.
 - Blood Draw: Any AE occurring within 24 hours after a study related blood draw.

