12.4.3 Recording Adverse Events

Throughout the study, the investigator will record adverse events and serious adverse events as described previously (Section 12.2, Definitions) on the appropriate AE/SAE eCRF regardless of the relationship to study therapy regimen or study procedure.

Once recorded, an AE/SAE will be followed until it resolves with or without sequelae, or until the end of study participation, or until 30 days after the subject prematurely withdraws (without withdrawing consent)/or is withdrawn from the study, whichever occurs first.

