7.3.2. Post-transplant Safety Endpoints

The safety sample will be used for analysis of these post-transplant safety endpoints.

Variable: Incidence and severity of infection episodes

Analysis: We will analyze each type of infection separately (bacterial, fungal, or viral, including RVI, CMV, and EBV), as well as for all types of infections combined. We will first determine the incidence of bacterial, fungal and viral infections in the rituximab and control groups using a combination of information from both the local, clinical site and the viral detection core laboratory. The presence of an infection at a given time point will be defined as follows:

- A local report of infection through either the organism specific CRF page or adverse event reporting;
- Presence of symptoms at the time of a study visit without a local report of infection but with a corresponding core lab identified infection.
 - All symptoms reported at the time of a study visit will be considered for any EBV and CMV infections identified by the core lab.
 - For any other infections identified in core lab NP and BAL samples, shortness of breath, new x-ray or other imaging finding, new supplemental oxygen requirement, cough with sputum, and decreased spirometry will be the only symptoms considered.

‘Incidence rate’ will be the number of infections per patient-month, and we will focus on the estimates and associated 90% confidence intervals for the ratio of such rates (RR), where $RR > 1.0$ indicates greater infection rates for rituximab. Of course, infection events are biologically related within patient, thus, relative to perfect independence of events, greater proportions of patients will experience more episodes of the same type of infection and greater proportions of patients will experience no episodes. Accordingly, Poisson regression models offset for months of follow-up and adjusted for overdispersion will be used to compare groups on the rate of each type of infection and any infection.

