The severity of infection episodes will be determined by reconciling all infections, as defined above, against those infections which qualified for adverse event (AE) reporting. Since the protocol restricts AE reporting to only those events which meet NCI-CTCAE grading criteria of Grade 3 or higher, any infections not reported as an AE will be assigned a severity of Grade ‘<3’ (effectively combining Grades 1 and 2); all other infections will utilize the assigned CTCAE severity grade of the corresponding AE. The proportion of subjects within each severity grade will be reported by treatment group with a corresponding 90% confidence interval; treatment groups will be compared using a Chi-square or Fisher’s Exact test. This presentation will be repeated for the number of events divided by person time, where time is the same across severity groups.

Variable: Serious adverse events (SAEs) related to rituximab

Analysis: For all SAEs, assessment of the relationship to rituximab will be made by the DAIT medical monitor. The proportion of subjects with SAEs determined to be related to rituximab will be reported by treatment group with 90% confidence intervals, and treatment groups will be compared using Chi-square or Fisher’s Exact test.

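### SAP 7.3.2 sets infections found only by the core laboratory to below Grade 3 without any severity assessment, so severity in that subset may be understated

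*SAP*

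**What the plan says.** SAP 7.3.2 admits an infection by two routes.

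- Local route: "A local report of infection through either the organism specific CRF page or adverse event reporting".
- Core-lab route: "Presence of symptoms at the time of a study visit without a local report of infection but with a corresponding core lab identified infection". For EBV and CMV any symptom at the visit counts. For other organisms the list is limited; it opens with shortness of breath and new imaging findings and ends "new supplemental oxygen requirement, cough with sputum, and decreased spirometry will be the only symptoms considered".

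Severity is then set by reconciling infections with AEs. The reason given is: "Since the protocol restricts AE reporting to only those events which meet NCI-CTCAE grading criteria of Grade 3 or higher". On that basis "any infections not reported as an AE will be assigned a severity of Grade" <3, while "all other infections will utilize the assigned CTCAE severity grade of the corresponding AE". The proportion of subjects in each grade is reported by arm with a 90% confidence interval and compared by chi-square or Fisher's exact test. The display is repeated for events per person-time.

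On what sites record, protocol 12.3.1 sends Grade 3 and higher events to the AE form, apart from an exception for cytopenias. Section 12.4.3 requires recording "regardless of the relationship to study therapy regimen or study procedure", and 12.5.1 requires all serious events to be reported whatever their relationship. Section 12.2.1, however, adds: "For this study, an adverse event will include any untoward or unfavorable medical occurrence associated with" the study drug or placebo, or study bronchoscopies and blood draws within 24 hours. Section 12.2.3 says that serious events falling outside its parameters should also be reported if the investigator sees a possible link to a protocol-mandated procedure.

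**The concern.** The default turns the absence of an AE into a grade. That is reasonable where a site recognised an infection, judged it mild and so filed no AE. It is not reasonable where the site did not identify an infection. For core-lab-only episodes the grade is unknown, and the rule records it as mild.

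Incidence and severity of infection is the first-listed safety outcome for a B-cell-depleting drug in children. Any error in this subset runs in one direction, towards lower severity, and it enters the between-arm comparison looking like an observed grade.

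**Working it through.** **1. Route and grade side by side (SAP 7.3.2)**

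| How the infection is known | Infection AE? | Grade under the SAP |
|---|---|---|
| Local, with an AE (core result positive or not) | Yes | AE's CTCAE grade |
| Local, organism page only | No | <3 |
| Core lab plus symptoms, no local report | None, because an AE is itself a local report | always <3 |

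In the third row the probability of Grade 3 or higher is zero by construction. The symptoms establish that an infection is present and are not used again for its grade.

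**2. Timing.** Protocol 9.6.1 has samples tested locally first, with the remainder frozen and sent to the core laboratory in batches. The site decides on AEs without the core result, so the absence of an infection AE does not show that the site judged the infection to be below Grade 3.

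**3. The SAP's other conventions.** SAP 8.1 rules out imputing missing safety data. SAP 7.2.1 uses an Unknown category for components that cannot be evaluated. SAP 8.2 gives AEs of unknown timing their own column. A fixed grade for an unassessed episode departs from all three.

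**4. The AE premise.** Sections 12.3.1, 12.4.3 and 12.5.1 support the inference that no AE means below Grade 3. Sections 12.2.1 and 12.2.3 can be read as narrowing what is recorded. A site reading them that way could enter a severe infection on the organism page alone, and the SAP would grade it <3.

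**5. Overlapping categories.** SAP 7.3.2 has no worst-grade rule. A child with one infection below Grade 3 and another at Grade 3 falls in two categories, whereas the between-arm test needs each child in one. SAP 8.2 already uses maximum severity for AEs.

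**6. Size.** The documents give no severity rate, no share of core-lab-only infections and no power for this endpoint, so there is no plan figure to reproduce. The following is illustration only.

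Inputs: 25 children per arm (50 randomized 1:1, protocol synopsis). Assumed: true proportions of children with a Grade 3 or higher infection of 30% (placebo) and 60% (rituximab), and a two-sided 10% level to match the 90% intervals. Let s be the share of those children whose only Grade 3 or higher infection is core-lab-only (assumed 0 to 30%).

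Observed proportion = true proportion × (1 − s).

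Chi-square power = Φ{[|p2 − p1| − 1.645 √(2p̄(1 − p̄)/25)] / √([p1(1 − p1) + p2(1 − p2)]/25)}, with p1 and p2 the observed proportions and p̄ their mean. Fisher power is by exact enumeration.

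| s, both arms | Observed | Risk difference | Risk ratio | Chi-square power | Fisher power |
|---|---|---|---|---|---|
| 0 | 30% vs 60% | 0.30 | 2.0 | 0.70 | 0.62 |
| 10% | 27% vs 54% | 0.27 | 2.0 | 0.62 | 0.54 |
| 20% | 24% vs 48% | 0.24 | 2.0 | 0.55 | 0.45 |
| 30% | 21% vs 42% | 0.21 | 2.0 | 0.48 | 0.37 |

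If s differs by arm, the ratio can move either way:

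- s = 10% placebo, 30% rituximab: (0.60 × 0.70)/(0.30 × 0.90) = 0.42/0.27 = 1.56.
- s = 30% placebo, 10% rituximab: 0.54/0.21 = 2.57.

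**The case against.** The strongest defence is that the SAP's inference rests on a recording duty. Grade 3 and higher events go on the AE form whatever their relationship, and hospitalization makes an event serious and reportable within 24 hours. A child with a severe respiratory deterioration should therefore have an AE even if no organism was identified, perhaps coded as a symptom. This largely stands. It justifies the default for locally recognised infections, subject to the reading of 12.2.1 and 12.2.3. It does not settle core-lab-only episodes, because the SAP does not say whether a symptom-coded AE counts as the corresponding one.

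Several stronger readings are tempting, and the documents do not support them.

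- That no core-lab infection can be severe. Core-positive infections with an AE take its grade.
- That a new oxygen requirement means Grade 3. No section says so; 12.3.1 describes Grade 3 only as severe and undesirable.
- That 12.2.1 excludes unrelated infections. It lists what an AE will include, its general definition covers unrelated events, and the 24-hour limit applies only to bronchoscopy and blood draws. It is unclear beside 12.4.3, no more than that.
- That a definite number of severe infections is lost. Protocol 2.4 reports 40 + 3 + 1 + 2 + 2 + 1 + 1 = 50 viral episodes in 31 CTOTC-03 children, or 50/31 × 50 ≈ 81 in 50 children. Assuming that 20–40% are symptomatic and unreported (16–32), and that 10–25% of those are severe, gives 2–8. Neither percentage is in the documents, and the detections are counted regardless of symptoms. Section 9.6.1 adds that core testing had not so far revealed treatable infections missed by sites in that study. Zero is plausible.

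It also stands that replacing the default for every infection without an AE would do harm. Grade 1 and 2 events are not collected as AEs, so nearly all mild, locally reported infections would become ungraded.

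**Conclusion.** The point holds for core-lab-only infections. Their grade is fixed below 3 with no assessment, so severity in this subset may be understated and cannot be overstated. A reader might infer that infection severity in the trial is understated. That follows only if some of these episodes were truly Grade 3 or higher and had no AE that counts as corresponding, which the documents do not show. The amount is unknown and may be zero.

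With sites blinded, similar misgrading in both arms is plausible. The risk ratio would then be unchanged, while the risk difference and power would shrink. In the illustration, chi-square power falls from 0.70 to 0.48 as s goes from 0 to 30%, under assumed rates only. Unequal misgrading could move the ratio either way. The infection incidence rates do not use the grade, and AEs, serious AEs and deaths are tabulated separately. This is an inexpensive improvement to a safety endpoint, not a defect that undermines the trial.

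**What to change.** 1. In SAP 7.3.2, keep <3 for locally reported infections with no AE.
2. For core-lab-only infections, while blinded, use the grade of any concurrent AE that matches in time and symptoms. State that a symptom-coded AE counts as corresponding. Show the remainder as not graded in their own row, flagging any concurrent hospitalization. Do not convert hospitalization to a CTCAE grade: in 12.2.3 it is a criterion for seriousness.
3. Add a sensitivity analysis that counts the not-graded infections first as all <3 (the current rule), and then with those that have a concurrent hospitalization counted as severe.
4. For the between-arm test, classify each child once, by worst grade.
5. Reconcile protocol 12.2.1 and 12.2.3 with 12.3.1, 12.4.3 and 12.5.1 on which infections must be recorded as AEs.

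The cost is SAP wording, a protocol clarification and one cross-check of data already captured (AEs and hospitalizations go on eCRFs under protocol 8.4). No new data collection is needed. The downside is a small not-graded row in the severity table.

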3.3. Secondary Endpoints

The following *secondary clinical endpoints* will be assessed:

1. Post-transplant outcomes including:
 - a) Incidence of chronic allograft dysfunction, relisting and death during the follow-up period, which will be a minimum of 12 months post-transplant;
 - b) Incidence of Primary Graft Dysfunction;
 - c) Incidence of Grade A Acute Rejection during the follow up period, which will be a minimum of 12 months post-transplant;
 - d) Incidence of Antibody Mediated Rejection during the follow up period, which will be a minimum of 12 months post-transplant;
 - e) Incidence of tacrolimus variability threshold during the follow up period, which will be a minimum of 12 months post-transplant;
 - f) Percentage of participants meeting tacrolimus variability threshold who complete tacrolimus variability intervention;
 - g) Magnitude of change in standard deviation of tacrolimus levels following intervention.
2. Post-transplant safety outcomes including:
 - a) Incidence and severity of infection episodes; See previous comment in the synopsis above
 - b) Serious adverse events related to rituximab.

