12.3 Grading and Attribution of Adverse Events

12.3.1 Grading Criteria

The study site will grade the severity of adverse events experienced by the study subjects according to the criteria set forth in the National Cancer Institute’s Common Terminology Criteria for Adverse Events (CTCAE) version 4. This document (referred to herein as the NCI-CTCAE manual) provides a common language to describe levels of severity, to analyze and interpret data, and to articulate the clinical significance of all adverse events. The NCI-CTCAE has been reviewed by the Protocol Chair and Principal Investigator and has been deemed appropriate for the subject population to be studied in this protocol.

Adverse events will be graded on a scale from 1 to 5 according to the following standards in the NCI-CTCAE manual:

Grade 1 = mild adverse event.

Grade 2 = moderate adverse event.

Grade 3 = severe and undesirable adverse event.

Grade 4 = life-threatening or disabling adverse event.

Grade 5 = death.

Events grade 1 and 2 will not be collected. Events grade 3 or higher will be recorded on the appropriate AE electronic case report form except for hematologic cytopenias. Only hematologic cytopenias meeting serious criteria outlined in 12.2.3 and occurring from the time of first rituximab infusion to 6 weeks following the last rituximab infusion will be collected and reported to the sponsor. Outside of this period, hematologic cytopenias meeting grade 3 and higher will be collected and reported to the sponsor.

For grading an abnormal value or result of a clinical or laboratory evaluation (including, but not limited to, a radiograph, an ultrasound, an electrocardiogram etc.), a treatment-emergent adverse event is defined as an increase in grade from baseline or from the last post-baseline value that doesn't meet grading criteria. Changes in grade from screening to baseline will also be recorded as adverse events, but are not treatment-emergent. If a specific event or result from a given clinical or laboratory evaluation is not included in the NCI-CTCAE manual, then an abnormal result would be considered an adverse event if changes in therapy or monitoring are implemented as a result of the event/result.

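### Infection severity is an ordered grade, but the SAP compares it with an unordered test, leaves the unit and table undefined, and names no between-arm severity estimate

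*SAP*

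**What the plan says.** Protocol 3.3 lists "Incidence and severity of infection episodes" as a secondary safety endpoint. Protocol 12.3.1 supplies the scale: "Adverse events will be graded on a scale from 1 to 5", running from mild to death. Only grade 3 and above are collected as adverse events, so SAP 7.3.2 pools the low end: "any infections not reported as an AE will be assigned a severity of Grade" <3, and "all other infections will utilize the assigned CTCAE severity grade of the corresponding AE". The result is four ordered levels: <3, 3, 4, 5.

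The analysis is then: "The proportion of subjects within each severity grade will be reported by treatment group with a corresponding 90% confidence interval", and the same sentence runs on: "confidence interval; treatment groups will be compared using a Chi-square or" Fisher's Exact test. The same presentation is repeated for events per person-time.

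Protocol 13.4.4 describes how infection rates will be analysed but gives no method for severity, so SAP 7.3.2 is the only specification. Protocol 13.4 says the clinical analysis will concentrate on hazard and risk ratios with two-sided 90% intervals comparing the arms on each endpoint.

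**The concern.** The question has a direction: are infections more severe on a B-cell-depleting drug? A Chi-square or Fisher's Exact test on the grades gives the same p-value if the labels <3, 3, 4 and 5 are shuffled. It therefore spends its power on patterns nobody is asking about.

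Three further gaps make the comparison hard to carry out or interpret:

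- **Unit.** No rule counts a child once. A child with one mild and one grade 3 infection belongs to two categories, and a single table built that way would not contain independent observations.
- **Table.** The text fits one overall table, or a separate two-by-two test for each grade. It also does not say whether children with no infection form a level.
- **Estimate.** The output is a set of within-arm percentages and a p-value. No between-arm measure of severity is named.

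At stake is the interpretation of a named safety endpoint in about 25 children per arm. A non-significant unordered test there carries little information about whether severity has shifted.

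**Working it through.** The documents state no power, effect size, alpha or expected grade distribution for infection severity, so there is no plan figure to reproduce.

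**Inputs from the documents**
- 50 randomized 1:1 (Protocol 3.1), so at most about 25 per arm.
- Four ordered levels (SAP 7.3.2).
- 90% intervals (SAP 7.3.2), which suggest two-sided alpha 0.10. No alpha is stated, so 0.05 is also shown.

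**Assumed inputs**
- Placebo worst-grade distribution for <3/3/4/5: 60/30/7/3 (%).
- A proportional-odds shift to worse grades. At each cut-point, rituximab odds of being at or below the cut = placebo odds / OR.

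**Shifted distribution at OR 3**
- At or below <3: 0.60/0.40 = 1.5; 1.5/3 = 0.5; probability 0.333.
- At or below 3: 0.90/0.10 = 9; 9/3 = 3; probability 0.75.
- At or below 4: 0.97/0.03 = 32.33; 32.33/3 = 10.78; probability 0.915.

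Rituximab is therefore about 33/42/17/8. The same steps at OR 4 give about 27/42/20/11.

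**Large-sample check.** A 1-df trend test with 80% power has noncentrality (z for alpha/2 + 0.842)². This is (1.960 + 0.842)² = 7.85 at alpha 0.05 and (1.645 + 0.842)² = 6.18 at alpha 0.10. Referred to a 3-df test with critical values 7.81 and 6.25, the power falls to 64% and 65%. The relative loss is about a fifth.

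**Simulation, 25 per arm, 60/30/7/3.** Pearson Chi-square against tie-corrected Wilcoxon; repeat runs agree to about 0.01.

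| Alpha | OR | Unordered | Rank | Relative loss |
|---|---|---|---|---|
| 0.10 | 3 | 0.47 | 0.65 | 1 - 0.47/0.65 = 28% |
| 0.10 | 4 | 0.67 | 0.83 | 1 - 0.67/0.83 = 19% |
| 0.05 | 3 | 0.34 | 0.53 | 1 - 0.34/0.53 = 36% |
| 0.05 | 4 | 0.53 | 0.72 | 1 - 0.53/0.72 = 26% |

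Using the exact version of each test at alpha 0.05 gives 0.37 against 0.52 (OR 3) and 0.55 against 0.71 (OR 4), losses of 29% and 23%.

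**Five levels (adding no infection).** Assumed placebo none/<3/3/4/5 of 15/35/35/10/5, 25/35/30/7/3 and 10/50/30/7/3. At alpha 0.05:
- OR 2: 0.11-0.13 against 0.25-0.27.
- OR 2.5: about 0.21 against 0.41, a loss of 1 - 0.21/0.41 = 49%.
- OR 4: 0.47-0.50 against 0.74-0.75, a loss of about a third.

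**If the SAP means one test per grade.** Four levels, OR 3, alpha 0.05: Fisher power is 0.41 for <3, 0.09 for grade 3, 0.07 for grade 4 and 0.01 for grade 5.

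**Shifts that are not proportional, alpha 0.10**
- 60/30/7/3 against 50/15/22/13 (grade 4-5 rises from 10% to 35%): Chi-square 0.58, rank 0.37.
- 15/35/35/10/5 against 25/20/20/25/10 (grade 4-5 rises from 15% to 35%): Chi-square 0.49, rank 0.16.
- 60/30/7/3 against 30/60/7/3 (movement from <3 to 3 only): 0.59 against 0.58, no loss.

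**The case against.** The strongest reply has four parts.

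**The ordinal gain depends on the shape of the shift.** Proportional odds is the setting that suits a rank test. When high grades rise but mild or no infection does not fall, the unordered test can win clearly, as the first two non-proportional cases show. This stands. A reader might infer that switching tests has no downside; the calculations do not support that, and it is why the fix adds high-grade risk differences.

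**Roughly half the power is lost.** A reader might infer this as a general figure. The documents do not support it: they contain no severity distribution or effect, and the SAP lists no level for no infection, so a single table has 3 degrees of freedom. Near-halving needs the extra level, alpha 0.05 and a modest odds ratio. Part of the gap is also conservatism of the Pearson test in sparse cells: with no effect it rejected about 3% of the time at nominal 5%.

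**Worst grade per child changes the quantity.** It drops repeat episodes and grows with follow-up, which runs from 1 to 4.5 years and is cut short by death. Placing no infection at the bottom mixes incidence with severity. These points stand in part. Randomization balances planned follow-up on average, the person-time presentation remains, and the overdispersed Poisson model in SAP 7.3.2 still analyses the rate separately.

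**Severity is visible elsewhere.** Per-grade percentages with intervals are reported whatever the test. There is a stopping rule for infections requiring hospitalization (Protocol 12.8.2.2), and SAP 8.2 tabulates adverse events by maximum severity. This limits the consequence, but none of these provides a between-arm estimate of infection severity.

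**Conclusion.** The concern holds in a limited form. It is certain from the text that the scale is ordered, the named tests ignore the order, the unit and table are undefined, and no between-arm severity estimate is specified.

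The size is conditional. With 25 per arm, four levels, a proportional shift with an odds ratio of 3 to 4 and the assumed 60/30/7/3 distribution, the unordered test loses about a fifth to a third of the ordinal test's power. The loss reaches about half only with five levels, an odds ratio of 2 to 2.5 and alpha 0.05. Under some non-proportional shifts it vanishes or reverses.

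This is a secondary safety analysis. It warrants a correction to the SAP, but nothing here bears on the primary endpoint.

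**What to change.** In SAP 7.3.2:

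1. Classify each child once, by worst infection grade, and state whether no infection is the lowest level.
2. Compare arms with a Wilcoxon rank-sum test or a proportional-odds model, and report the common odds ratio with its 90% interval.
3. Keep the per-grade percentages as description, without a test for each grade.
4. Add the between-arm risk difference with 90% interval for grade 3 or higher and for grade 4-5.

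Item 4 covers the case where an excess of severe infection is not a uniform shift. It will be imprecise: if 40% of each arm had grade 3 or higher (an assumption), the half-width would be 1.645 × √(2 × 0.4 × 0.6 / 25) = 0.23. The interval would at least show that imprecision, which a p-value alone would not.

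The cost is a few lines of SAP text and one changed procedure, with no new data. The downside is small: possible loss of power under non-proportional shifts, and mixing of incidence with severity if no infection is a level. Item 4 and the existing Poisson rate analysis cover these.

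### SAP 7.3.2 gives no method that allows for within-child correlation when infection event rates are broken down by severity, although it states that correlation and models it for infection type

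*SAP*

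**What the plan says.** SAP 7.3.2 (Post-transplant Safety Endpoints) deals with infection in two parts.

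- **Rates by infection type and for any infection.** The section notes that "infection events are biologically related within patient" and for that reason chooses a model, to be run by infection category and for all infections pooled: "Poisson regression models offset for months of follow-up and adjusted for overdispersion will be used to compare groups on the rate of each type". Results are rate ratios with 90% intervals. Protocol 13.4.4 has the same model and gives no method for severity.
- **Severity.** An infection not reported as an adverse event is classed as below grade 3; the others take the CTCAE grade of the matching adverse event. Then: "The proportion of subjects within each severity grade will be reported by treatment group with a corresponding 90% confidence interval". The arms are tested against each other on these proportions by Chi-square or Fisher's exact test. The paragraph ends: "This presentation will be repeated for the number of events divided by person time, where time is the same across severity groups".

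That last sentence is all the SAP says about analysing severity-specific event rates.

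**The concern.** The severity paragraph moves from children to events without changing method. For proportions of children, a Chi-square or Fisher test is sound, because each child can be counted once. For numbers of events, one child may contribute several infections. A test or simple interval that treats events as independent then understates the variance. The SAP identifies this problem, adopts a remedy for infection type, and does not extend the remedy to severity.

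At stake is the comparison of severe infection rates when B-cell depletion is added to Thymoglobulin induction. Severity is part of the named safety endpoint, and infection requiring hospitalization is a stopping-rule trigger (Protocol 12.8.2.2). With 50 children, an interval that is too narrow could suggest harm, or give reassurance, by chance. Follow-up runs from 12 to 54 months (Protocol 11.1), so a test on raw counts could also ignore unequal person-time.

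**Working it through.** The documents give no error rate or precision for this comparison, so there is no planned figure to reproduce. The check sets out which method covers what, then sizes the error if simple methods were used on event counts.

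**Coverage of methods in SAP 7.3.2**

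| Quantity | Unit | Method given |
|---|---|---|
| Rate by infection type, and any infection | events per patient-month | Poisson, follow-up offset, overdispersion-adjusted |
| Proportion by severity grade | child | 90% CI; Chi-square or Fisher |
| Rate by severity grade | events per person-time | the same presentation repeated; no test or interval method named |

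**Inputs**

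- 50 children randomized 1:1, so 25 + 25 (SAP synopsis).
- 90% intervals (SAP 7.3.2). No significance level is stated for the severity test; 5% is used for illustration.
- φ, the variance-to-mean ratio of infections per child. The documents do not give it. Assumed values are 1.5, 2 and 3.

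**A rough guide to φ.** Protocol 2.4 reports on the CTOTC-03 cohort. Listed detections are 40+3+1+2+2+1+1 = 50. Over 31 children that is 50/31 = 1.61 each. Eight of the 31 had none (25.8%), against exp(−1.61) = 19.9% under a Poisson distribution. Solving (1 + 1.613/k)^(−k) = 0.258 for a negative binomial gives k = 3.99, so φ = 1 + 1.613/3.99 = 1.40. This assumes that every listed number counts episodes, that all come from the same 31 children, and that follow-up was equal. It covers viral detections of any severity.

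**Thinning to grade 3 or higher.** If a fraction p of infections is grade 3 or higher, independently within child, the ratio for that subset is 1 + p(φ − 1). With p = 0.3 (assumed):

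- φ = 1.5: 1 + 0.3 × 0.5 = 1.15
- φ = 2: 1 + 0.3 × 1 = 1.30
- φ = 3: 1 + 0.3 × 2 = 1.60

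**Error and coverage.** With equal person-time and event totals A and B, the simple statistic is (A − B)²/(A + B). The true variance of A − B is φ times what this assumes, so:

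- test error = 2[1 − Φ(1.96/√φ)]
- coverage of a nominal 90% interval = 2Φ(1.645/√φ) − 1

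| φ for the events analysed | 1.96/√φ | Error at nominal 5% | 1.645/√φ | Coverage of nominal 90% CI |
|---|---|---|---|---|
| 1.00 | 1.960 | 5.0% | 1.645 | 90.0% |
| 1.15 | 1.828 | 6.8% | 1.534 | 87.5% |
| 1.30 | 1.719 | 8.6% | 1.443 | 85.1% |
| 1.60 | 1.549 | 12.1% | 1.300 | 80.7% |
| 1.50 | 1.600 | 11.0% | 1.343 | 82.1% |
| 2.00 | 1.386 | 16.6% | 1.163 | 75.5% |
| 3.00 | 1.132 | 25.8% | 0.950 | 65.8% |

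The 1.15 to 1.60 rows are the thinned case; the last three apply if there is no thinning benefit. At a nominal 10% level the test error is 100% minus the last column.

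**Simulation check.** Negative binomial counts were simulated for 25 + 25 children, with means of 1, 1.61 and 3 per child and 20,000 runs per setting. The simple test on event totals agreed with the formula within about one percentage point. An overdispersion-adjusted Poisson comparison had 9.6% to 10.3% error at nominal 10%, and 4.6% to 5.1% at nominal 5%, for φ from 1 to 3. A subject-level test (any infection, yes or no) stayed at about 7% to 12% at nominal 10%. Means below 1 per child were not simulated, so behaviour with very few severe events is untested.

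**The case against.** The strongest reply is that the SAP attaches Chi-square or Fisher to proportions of subjects, where repeat infections do no harm. The sentence on person-time names no test, and such a test is not defined for a rate without a further step that the SAP does not give. The repeat may be only a second descriptive table. This stands as far as it goes. A reader might infer that the SAP specifies a Chi-square or Fisher test on event counts, or that its written intervals are too narrow. The documents do not support either statement: carry-over of the test is a natural reading but not the only one, and no interval method for these rates is written. What remains is that the intervals are part of the presentation to be repeated, and on either reading nothing given for them allows for clustering. Holding person-time equal across grades settles the denominator, not the correlation.

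A second reply is that the main infection-rate comparison already uses the overdispersed model. That is true, and it limits the point to the breakdown by grade.

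A reader might also infer that a persistent infection is counted repeatedly among severe events, because SAP 7.3.2 defines infection at a given time point. For grade 3 or higher this is not well supported. Those infections take their grade from adverse events, which SAP 8.2 records once at the highest severity and Protocol 12.4.3 follows to resolution, the end of participation or 30 days after withdrawal. The SAP does not say whether several time points could map to one adverse event, but a rule merging consecutive positives for the same organism could join separate infections found at visits months apart, so none is proposed.

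Finally, rarer events usually show less overdispersion. That is accepted, and is why the thinned figures are shown.

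**Conclusion.** The point holds as a gap in method, conditional in size. SAP 7.3.2 states that infections within a child are related, models that for infection type and any infection, and leaves severity-specific rates without a method that allows for it.

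If simple methods are used on event counts, the error at nominal 5% is about 7% to 12% and 90% coverage about 87.5% to 81% for a variance inflation of 1.15 to 1.6. It is 11% to 26% and 82% to 66% for 1.5 to 3. The lower range assumes that 30% of infections are grade 3 or higher and that grade is independent within child; correlated grades would move the figures up. All inflation values are assumptions, and the cohort-based 1.4 is only a guide.

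This affects a secondary safety summary. The primary analysis and the infection comparisons by type are not affected.

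**What to change.** In SAP 7.3.2:

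1. State that Chi-square or Fisher applies only to subject-level proportions, with each child classified once by worst infection grade.
2. For event rates, fit the Poisson model already planned in that section (log person-months offset, overdispersion-adjusted) to grade 3 or higher infections. Report the rate ratio with its 90% confidence interval.

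No new data are needed. The cost is two sentences of SAP text, one more run of a planned model, and somewhat wider intervals.
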